# 7.8 Criteria for Drop-out Cases

- Subjects withdraw by themselves (conscious efficacy is too poor, adverse reactions, etc.);
- 869 (2) Lost to follow-up;

862

863

864

865

866

875

- The investigator advised her to withdraw (poor compliance, serious comorbidities or complications, serious adverse events).
- The reasons for dropout should be recorded in detail, and the last primary efficacy test result should be transferred to the final result for statistical analysis. The eCRF should be retained for future reference.

876	8 STUDY DRUG
877	8.1 Information about the study drug

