# **6.5 Efficacy Assessments**

Response to tumor therapy will be assessed in this study using Response Evaluation Criteria in Solid Tumors RECIST v1.1, see Appendix II.

The primary outcome measure of Ib trial is objective response rate (ORR), the proportion of subjects with confirmed overall CR and confirmed overall PR in all subjects who have received the study drug.

Progression-free survival (PFS) for this study is defined as the time from the start of treatment with MRG003 until objective tumor progression or death from any cause. Duration of response (DOR) is defined as the time from the first documented response until disease progression or death among subjects with a confirmed objective response (CR or PR), with tumor evaluation according to RECIST v1.1 criteria. Overall survival (OS) is defined as the time from the start of treatment with MRG003 to death due to any cause.

For patients without disease progression after the last dosing cycle, tumor response should be assessed every 6 weeks and followed up for survival until disease progression or other anti-tumor treatment. Survival follow-up could be performed every 12 weeks after confirmation of disease progression or receipt of additional antineoplastic therapy. The follow-up period starts from the end of treatment cycle until death or study termination. During follow-up, survival status and subsequent tumor treatment need to be examined and recorded. Subsequent tumor treatment does not need to be recorded in electronic case report form (eCRF).

Tumor evaluation will be performed according to RECIST v1.1, and the results of imaging assessment methods should be recorded in the electronic case report form. During trial treatment, radiographic assessments may be performed  $\pm$  7 days from the scheduled date and the methodology should be consistent between baseline and subsequent follow-up. Whenever clinically permissible, the same oral or intravenous contrast agent was used for each scan, and, whenever possible, the same investigator/radiologist evaluated all patient scans during the study.

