#### 7.5 Subject Withdrawal Criteria

#### 7.5.1 Investigator's decision to withdraw a subject

Withdrawal of a subject from the trial refers to that the enrolled subject suffers from conditions unsuitable for continuation of the trial during the trial. The investigator decides to withdraw the subject from the trial, and the investigator decides to withdraw the subject from the trial for diagnosis and treatment measures.

- 815 (1) Unequivocal disease progression;
- 816 (2) Subject died;

793

794

795

796 797

798

799

800

803

804

805

806

807

808

809

810

811

812

813

814

- The subjects with adverse events and serious adverse events who are not suitable for continuation of the trial as judged by the investigator should continue to be followed up for 21 days or until the adverse reactions are relieved or recovered;
- Use of other therapies or drugs that affect the efficacy and safety judgment;
- Patients with poor medication compliance who cannot make a visit on time during two consecutive visit time windows.

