# 7.5.2 Withdrawal by subject

823

824

825

826 827

828

829830

831

832

833

834

835

836

837

838

839 840

841

855

According to the Good Clinical Practice (GCP), subjects have the right to withdraw from the study at any time for any reason, or they are lost to follow-up due to failure to observe and test the investigational drug but do not explicitly propose to withdraw from the study, which also belongs to "withdrawal" or "dropout". For subjects withdrawing from the trial, the reason for withdrawal should be known as much as possible and recorded in the eCRF. Possible reasons: withdrawal of the ICF; perceived poor efficacy; intolerance to some adverse reactions; inability to continue the clinical study due to work or life effects; loss to follow-up due to economic factors or unexplained reasons.

Regardless of the reasons, for the subjects who withdraw from the trial, the records of their last subject visit/follow-up cases (including laboratory tests and test indicators) should be retained, and the efficacy and adverse reactions should be analyzed in the full data set by taking them as the last test results and transferring them into the final results.

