# 8.2 Dose Modifications, Modifications, and Delays

The investigator may delay the administration of study drug due to toxicity of study drug. Once a dose delay occurs, the scheduled time for subsequent doses should be adjusted later. However, if a subject delayed dosing for > 3 weeks (1 dosing cycle), the subject was considered withdrawn from the trial.

The investigator may also adjust the dose of study drug because of study drug toxicity, and a maximum of 2 dose reductions is allowed. However, patients in the initial dose 0.1 mg/kg group were not allowed to reduce the dose during the experiment, and patients in the second dose 0.3 mg/kg group were only allowed to reduce the dose once to 0.1 mg/kg during the experiment. If the subject is still intolerable after dose reduction for 2 times, the drug should be permanently discontinued and the patient should withdraw from the trial. If a subject's dose is reduced, subsequent doses will be adjusted according to the new dose, and re-escalation is not allowed.

Table 5: Dose Modification Table

Dose Level	MRG003 Dose
Dose Level	MRG003 Dose

	- 1	Previous Dose											
	- 2	First two doses											
•	If a subject	t delayed dosing for > 3 weeks, the subject was considered withdrawn ial											
•	If a subject required a dose reduction > -2 dose levels, the subject was permanently discontinued from the trial												

- A subject may require a dose reduction for any of the following adverse events:
  - For CTCAE v4.03 grade 3 to 4 non-hematologic adverse events related to drug toxicity that cannot be resolved to grade 2 or less within 72 hours after supportive care, study drug dose reduction is required. However, the investigator can determine to what extent the dose of the study drug can be not adjusted for adverse reactions that will not cause damage to vital organs, such as alopecia, which is recovered after supportive treatment;
  - Grade 4 neutropenia lasting > 5 days;
- Febrile neutropenia;

- Grade 4 thrombocytopenia;
- Grade 2 irreversible peripheral sensory nerve abnormalities; Grade 2 or higher neurological diseases, which still fail to return to the baseline level within 4 weeks after administration after supportive treatment;
  - Other adverse events decided by the investigator;

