#### 9.8 Early termination of treatment

- 1151 Treatment of a subject may be discontinued early in the following circumstances:
- In case of uncontrolled adverse events, the investigator decides to stop treatment;
- The subject experienced disease progression;
- Subject died;
- Withdrawal of informed consent by the subject;
- Subject lost to follow-up.

In any case of premature treatment discontinuation, the investigator should make every effort to inquire about the reason for premature treatment discontinuation and record the discontinuation on the subject's eCRF form. When a subject prematurely discontinues treatment due to an AE/SAE, the investigator should follow the subject until the condition is cured or stable, and continue to complete imaging assessments and survival follow-up.

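### Sections 7.5.2 and 7.8 carry a leaver's last efficacy result into the final result, which contradicts the confirmed best response that defines the Phase Ib ORR

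*Protocol*

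**What the plan says.** **The carry-forward rule.** Section 7.8 covers subjects who withdraw by themselves, are lost to follow-up, or are advised by the investigator to leave. For them, "the last primary efficacy test result should be transferred to the final result for statistical analysis". Section 7.5.2 opens its rule with "Regardless of the reasons, for the subjects who withdraw from the trial" and goes on: "the efficacy and adverse reactions should be analyzed in the full data set by taking them as the last test results". Section 14.3 defines a Safety Set, an Evaluable Analysis Set and a PK Analysis Set. It does not define the set that 7.5.2 names; a full analysis set appears only in the list of abbreviations.

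**The endpoint.** Section 6.5 makes the Phase Ib primary measure the proportion with "confirmed overall CR and confirmed overall PR" among all who received study drug. Section 14.4.4.2 summarises best response over the whole trial and requires two assessments to confirm it. Section 14.3 assigns the primary efficacy analysis to the Safety Set. Section 14.4.3.2, which describes the primary analysis, gives only CR plus PR over the number in the analysis set. It mentions neither confirmation nor best response.

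**Leaving the trial.** Section 7.5.1 lists "Unequivocal disease progression" first among the investigator's reasons for withdrawing a subject. Section 8.2 says that "if a subject delayed dosing for > 3 weeks (1 dosing cycle), the subject was considered withdrawn from the trial". The synopsis ends the 6-weekly efficacy follow-up at withdrawal, among other events. For subjects who stop treatment early because of an AE or SAE, section 9.8 requires the investigator to "continue to complete imaging assessments and survival follow-up".

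**The concern.** The last result and the best confirmed result are different quantities, and they diverge in the subjects who leave. The Phase Ib ORR is the primary outcome, and 7.8 refers expressly to the primary efficacy result, so the sentence cannot be dismissed as concerning something else. A programmer who follows section 7 and one who follows sections 6.5 and 14.4.4.2 could report different ORRs from the same scans, and both could point to protocol text.

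With 12 subjects per tumor type, moving even one subject is visible in the estimate. The conflict also reaches duration of response. Section 6.5 measures DOR among confirmed responders up to progression or death. Under carry-forward, a responder withdrawn at progression could contribute a DOR event and still be scored as a non-responder.

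**Working it through.** The protocol gives no assumed response rate, power or drop-out rate, and 14.1 says that the sample size has no formal basis. There is no derived figure to reproduce; 3 × 12 = 36 agrees with the stated Phase Ib total. The check is to follow subjects through both rules and then size one reclassified subject.

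**Inputs**
- Cohort size 12, Phase Ib total 36 (14.1).
- Confirmation 6 weeks after the first CR or PR (notes to Table 6; 9.6 item 6).
- Denominator: all treated subjects (6.5), which is the Safety Set (14.3).

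**Subject A: first PR on scan, then lost to follow-up before the confirming scan**
- 6.5 and 14.4.4.2: no confirmed response, so a non-responder who stays in the denominator.
- 7.8: the last result is PR and becomes final, so a responder.
- This arises in Phase Ib only. Section 14.4.4.1 does not require confirmation in Phase Ia.

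**Subject B: confirmed PR, later PD, then leaves**
- 6.5 and 14.4.4.2: the best response is a confirmed PR, so a responder.
- 7.5.2: the last result is PD and becomes final, so a non-responder.
- There are two routes into this case. Either the all-reasons wording of 7.5.2 reaches the progression withdrawals of 7.5.1, or the subject chooses to leave for perceived poor efficacy, which both 7.5.2 and 7.8 list. Section 7.8 does not list progression itself.

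**Size of one reclassification**
- One cohort: 1/12 = 8.3 percentage points.
- All three cohorts pooled, if they are pooled: 1/36 = 2.8 points.

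**Illustration.** All response counts here are assumptions; the protocol gives none. Take a cohort of 12 with 3 confirmed responders. Let u be the number of type A subjects and d the number of type B. The carried-forward ORR is (3 + u − d)/12. Intervals are exact (Clopper-Pearson) 95%.

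| u | d | ORR | 95% CI |
|---|---|---|---|
| 0 | 0 | 3/12 = 25.0% | 5.5 to 57.2 |
| 1 | 0 | 4/12 = 33.3% | 9.9 to 65.1 |
| 2 | 0 | 5/12 = 41.7% | 15.2 to 72.3 |
| 0 | 1 | 2/12 = 16.7% | 2.1 to 48.4 |
| 0 | 2 | 1/12 = 8.3% | 0.2 to 38.5 |
| 1 | 1 | 3/12 = 25.0% | 5.5 to 57.2 |

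In the last row the two errors cancel in the estimate, although two subjects are misclassified. The sign of the net error depends on u − d, which the document cannot supply.

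**The case against.** The strongest reply is that the endpoint is already fixed where it belongs. Section 6.5 defines the Phase Ib ORR, 14.4.4.2 requires confirmed best response, and 14.3 names the primary set. Read alone, these make subject A a non-responder and keep subject B a responder. On this view the sentences in section 7 are generic withdrawal text that yields to the specific definition. This stands in part: the ORR is wrong only if 7.5.2 and 7.8 are taken to override 6.5 and 14.4.4.2. But the protocol never says that they yield, and 14.4.3.2 does not settle it. The Evaluable Analysis Set does require two assessments at least 4 weeks apart for Phase Ib responders, but it serves only the secondary efficacy analyses.

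A second reply is that 7.5.2 is headed as withdrawal by the subject, while progression appears in 7.5.1, which has no carry-forward sentence. That is a fair reading. It narrows the downward error without removing it, because a subject who has progressed may leave for perceived poor efficacy.

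Third, Phase Ib is exploratory and an SAP not shown could state precedence. It could, but the conflicting text would remain in the protocol, and 14.2 requires both documents to be amended when methods for the primary objectives change.

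Two stronger readings are tempting but unsupported.
- **Adverse events.** A reader might infer that carrying forward adverse reactions hides the worst grade. Section 11.5.1 records every AE with its severity, and 14.4.5 counts and grades all treatment-emergent events. Nothing replaces an earlier grade with a later one.
- **Overall survival.** A reader might infer that 8.2 causes OS follow-up to be lost selectively in subjects with toxicity. Survival follow-up runs to death or loss to follow-up in the synopsis and to death or study termination in 9.7, and 9.8 explicitly continues it after stopping for an AE.

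**Conclusion.** The concern holds as an internal contradiction in the protocol about the Phase Ib primary endpoint. Sections 7.5.2 and 7.8 score the last result; 6.5 and 14.4.4.2 score confirmed best response; no text ranks them; and 7.5.2 applies its rule in a set that 14.3 does not define.

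The size is 8.3 points of cohort ORR per reclassified subject, on the condition that carry-forward is applied to the ORR. The upward error is confined to Phase Ib. The downward error depends on the scope of the all-reasons wording in 7.5.2 or on the subject's stated reason for leaving. The document does not support a claim that the ORR will be biased in a particular direction, or by the amounts in the illustration.

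A secondary wording conflict also stands. A subject whose dosing is delayed for toxicity beyond the limit in 8.2 counts as withdrawn from the trial. The synopsis ends efficacy follow-up at withdrawal, while 9.8 continues imaging after stopping for an AE. This leaves unclear whether scans for PFS and DOR continue; it does not show that they stop.

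**What to change.** 1. Delete the efficacy carry-forward wording in 7.5.2 and 7.8, and with it the reference to an undefined analysis set.
2. In 14.4.3.2, state that the Phase Ib ORR uses confirmed best overall response in the Safety Set, that a treated subject without a confirmed CR or PR counts as a non-responder (early leavers included), and that a confirmed responder remains a responder after later PD.
3. Reconcile the withdrawal wording in 8.2 and the synopsis rule on efficacy follow-up with the continued imaging and survival follow-up in 9.8. Distinguishing the end of study treatment from withdrawal from the trial would do this. The treatment-stopping rule itself is left as it is.

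The cost is a protocol wording amendment, with matching SAP text. Sample size does not change. Any additional scans or survival contacts are those that 9.8 already requires.

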# 8.1.1 Study Drug Shipment and Transfer

The product was manufactured and packaged under GMP conditions and stored and transported at 2-8°C in the dark. The drug will be provided by the sponsor and handed over to CRO, which will be responsible for the storage and transportation of the drug.

#### 8.1.2 Study Drug Ingredients, Appearance, Packaging, and Labeling

The pharmaceutical components of MRG003 for injection include MRG003. Its active ingredient is recombinant humanized anti-EGFR monoclonal antibody-vcMMAE conjugate (MRG003).

MRG003 drug product is supplied as a white to off-white loose mass in a single-use vial with the label claim of 20 mg/vial and packaged as a box of 1 vial. It is a colorless to slightly yellow, clear to slightly opalescent solution after dissolution for intravenous drip. The MRG003 concentration after dissolution is 4 mg/mL.

# 8.1.3 Study Drug Storage and Stability Testing

The product should be stored and transported at 2-8°C, protected from light.

Shelf life of reconstituted solution

The product is stable for 24 hours at room temperature and  $2 \sim 8$ °C after dissolution with sterile water for injection. The solution remaining after 24 hours should be discarded.

Validity period of the solution for infusion containing the reconstituted solution

The reconstituted MRG003 solution was diluted with 0.9% sodium chloride in normal saline to the drug concentration of 0.2-3.0 mg/mL, and was stable for 24 hours at room temperature. Since the diluted MRG003 solution does not contain preservatives, the prepared solution should be used as soon as possible, and the remaining solution after more than 24 hours should be discarded.

Do not use after the expiration date shown on this product.

#### 8.1.4 Study Drug Preparation

Each vial is reconstituted with 5 mL of Sterile Water for Injection before use and is a colorless to slightly yellow, clear to slightly opalescent solution, free of visible particles.

Prior to administration, withdraw the appropriate volume of MRG003 reconstituted solution and slowly inject into a flexible bag or bottle of 0.9% Sodium Chloride Injection and gently invert several times to thoroughly mix the solution to avoid excessive foam

during mixing. The mixed solution is intravenously infused into the patient's body for 30 minutes to 3 hours.

#### 8.1.5 Dose and Schedule

According to the actual body weight of the subjects, administration was designed according to the dose in this clinical protocol.

#### 8.1.6 Administration method and administration period

MRG003 will be administered as an intravenous infusion on Day 1 of each cycle.

Each MRG003 dosing cycle is every 3 weeks (Q3W). Each subject received up to 8 dosing cycles throughout the study.

Prior to the start of each dosing cycle, subjects must meet the following conditions to receive intravenous infusion of MRG003:

- Neutrophil count  $\geq 1.5 \times 10^9/L$  and platelet count  $\geq 75 \times 10^9/L$ . Supportive therapy was allowed to improve the subject's hematologic condition (except prior to the first dose).
- Adverse reactions related to study drug must have improved to baseline or CTCAE v4.03 grade ≤ 1. For adverse reactions that do not result in fatal organ damage, such as hair loss, the investigator may decide whether the drug can be administered to the subject.

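### Section 8.1.6 exempts any reaction short of fatal organ damage from the re-dosing hold, so read literally the baseline or grade 1 rule is discretionary for most non-fatal organ toxicity

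*Protocol*

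**What the plan says.** Section 8.1.6 of the protocol introduces its re-dosing rule with mandatory language: before each cycle "subjects must meet the following conditions to receive intravenous infusion of MRG003". Two conditions follow.

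- **Blood counts.** Neutrophils must be at least 1.5 × 10⁹/L and platelets at least 75 × 10⁹/L. Supportive therapy may be used to reach these values, except before the first dose. No investigator exemption is attached.
- **Recovery from toxicity.** "Adverse reactions related to study drug must have improved to baseline or CTCAE v4.03 grade ≤ 1". The exemption comes directly after this: "For adverse reactions that do not result in fatal organ damage, such as hair loss, the investigator may decide" whether the subject can be dosed.

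The rule applies at every cycle: "Each subject received up to 8 dosing cycles throughout the study".

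Section 8.2, on dose reduction, has a parallel exemption with the same example. There the investigator's latitude covers "adverse reactions that will not cause damage to vital organs, such as alopecia, which is recovered after supportive treatment".

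**The concern.** The exemption turns on whether organ damage is fatal. Hardly any reaction in a patient who has come back for the next infusion meets that description. Taken at its word, the clause therefore returns to the investigator almost everything that the preceding sentence holds.

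MRG003 is a cytotoxic (MMAE) conjugate being given to humans for the first time. Section 4.2.2.2 reports that an approved antibody to the same target bound human corneal, liver and bronchial epithelium, and that MRG003's own tissue cross-reactivity results were generally consistent with this. Exclusion criterion 6 keeps out patients at raised risk of corneal damage. Non-fatal organ toxicity is thus a risk that the protocol itself foresees. If the dosing text lets it be dosed through, two sites can treat the same patient differently and both comply. Section 7.2 adds further sites in Part Ib.

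**Working it through.** No arithmetic applies. The check has two parts: what the exemption covers, and whether another fixed rule closes the gap.

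**1. The two exemptions side by side**

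| | Section 8.1.6 | Section 8.2 |
|---|---|---|
| Decision governed | whether to give the next dose | whether to reduce the dose |
| Reactions exempted | those not resulting in fatal organ damage | those not damaging vital organs |
| Example | hair loss | alopecia |
| Added condition | none | recovered after supportive treatment |
| Upper grade | none stated | none stated |

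The example is the same but the test differs. An unresolved grade 2 rise in liver enzymes is not fatal organ damage, so it falls inside the 8.1.6 exemption. It does involve a vital organ, so a test in the 8.2 wording would normally leave it under the hold.

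**2. Whether another fixed rule holds a grade 2, non-neurological organ reaction**

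- *Blood-count minimums (8.1.6).* They bind, but cover neutrophils and platelets only.
- *Dose delay (8.2).* The investigator may delay, so this is permissive. The withdrawal rule for delays of more than 3 weeks applies only once someone has chosen to delay.
- *Dose reduction (8.2).* Six triggers are listed. They set the dose level and do not decide whether the subject may be dosed:
  1. Grade 3 to 4 non-hematologic events "that cannot be resolved to grade 2 or less within 72 hours after supportive care, study drug dose reduction is required". The trigger does not apply once the event is at grade 2 in time.
  2. Grade 4 neutropenia for more than 5 days.
  3. Febrile neutropenia.
  4. Grade 4 thrombocytopenia.
  5. "Grade 2 irreversible peripheral sensory nerve abnormalities; Grade 2 or higher neurological diseases, which still fail to return to the baseline level" within 4 weeks. This is the only named event set at grade 2, and it is neurological.
  6. "Other adverse events decided by the investigator", which is discretion again.
- *No-DLT condition for Cycle 2 (9.5).* It applies to Part Ia only, and only to the step from Cycle 1 to Cycle 2. The organ criteria in Table 4 are set mainly at grade 3 or above, so a grade 2 reaction is not in itself a DLT. Section 9.6 states no such condition for Part Ib.
- *Withdrawal or early stopping for adverse events (7.5.1, 9.8).* Both rest on the investigator's judgment.
- *Laboratory checks before each cycle (Table 6, note h).* They are there to confirm eligibility for dosing. The only numeric laboratory minimums in 8.1.6 are the two blood counts, so for other tests the check leads back to the recovery sentence and its exemption.
- *SMC supervision (6.3.5).* This is general oversight and gives no per-patient re-dosing rule.

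**Result.** For an unresolved grade 2 organ reaction that is not neurological, the baseline or grade 1 hold in 8.1.6 is the only fixed re-dosing rule, and the exemption as worded makes it optional.

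**The case against.** The strongest reply is that nobody would read the clause this way. If the hold bound only where organ damage was fatal, it would bind only where re-dosing could not arise, and the mandatory sentence before it would be empty. Hair loss shows the class intended, and 8.2 confirms it. The English text also bears marks of translation, such as the misrendered column headings in Tables 7-1, 7-2 and 8. The version used at the sites may not have the defect, and the documents do not allow that to be checked. This stands as evidence of intent, and it is why the point is put as a probable slip. It does not repair the text: dosing over a non-fatal organ toxicity would comply with the rule as printed.

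A second reply is that the protocol has many other safeguards. It does, and they are listed above. They reduce the risk but do not restore a fixed hold.

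Three stronger readings are tempting, and the documents do not support them.

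- *That 8.1.6 and 8.2 contradict each other.* They govern different decisions, so this is a mismatch between parallel exemptions.
- *That DLT counts or the MTD are affected.* A reader might infer this because Table 4 counts a delay of more than 14 days for toxicity not back to grade 1 or baseline, and a discretionary hold could avoid such a delay. Nothing in the protocol shows that this would happen, or how often. An effect on ORR has no better support.
- *That subjects times cycles measures the problem.* The clause matters only where a drug-related reaction is still above both grade 1 and baseline, and no frequency is given for that. Even an upper limit is not fixed. About 26 subjects are expected in Part Ia, but Table 2 allows 1 + 1 + 6 × 6 = 38 at the planned levels.

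**Conclusion.** The point holds as a defect of wording in an operative safety rule. As printed, the recovery hold in 8.1.6 is discretionary for almost any unresolved non-fatal reaction outside the neutrophil and platelet minimums, and no other fixed rule holds a grade 2 organ reaction that is not neurological. The conclusion assumes that the English text is the one applied and that *fatal* is read as describing the damage. If the site version already refers to vital organs, only the English needs correcting. The consequence is a weaker and less uniform safeguard for patients. It does not impair the trial's estimates, and its size cannot be quantified from the protocol. It should be corrected because the remedy is nearly free.

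**What to change.** In Section 8.1.6, replace the words about fatal organ damage so that the exemption covers reactions that *will not cause damage to vital organs (the eye included)*, and keep the hair-loss example. This brings the clause into line with 8.2. The parenthesis is needed because it is open to argument whether the eye is a vital organ, and ocular toxicity is foreseeable with this target.

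The change sets no hemoglobin minimum, so it does not settle re-dosing with anemia. A grade cap or a closed list of exempt reactions would be tighter, but it would be a new design decision and is not needed to restore the evident intent.

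The cost is one phrase in a protocol amendment, with no new data or visits. The downside is slightly less investigator discretion. Discretion for minor toxicity remains.
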